7.3.4 Visit 6 (Day 57) exit evaluation

The end of study visit (Visit 6) will be conducted in the clinic 56 days following the first administration of IMP. The following tests will be performed and documented as indicated on the CRF:

- Symptom directed physical examination (See Section 7.4.1)
- Vital Signs (See Section 7.4.1)
- DAS28CRPv4 Evaluation
- Blood samples for:
 - Haematology including ESR (See Section 7.4.3)
 - Clinical chemistry including CRP(See Section7.4.3)
- Urine samples for urinalysis and pregnancy testing (See Section7.4.3)
- An oral swab will be taken (See Section 7.4.8)
- Blood Samples for Immunological Assessment including (see Sections 7.4.3 and 7.4.4):
 - Anti-CCP2 (See Section 7.4.3)
- Adverse event and concurrent medication questioning (see sections 9 and 10)

7.4 Details of scheduled assessments

7.4.1 Demographic data, medical history, physical examination, vital signs

Demographic data will include sex, race/ethnicity and date of birth.

The medical history will include any diagnosed medical conditions or surgical history.

A complete physical examination (including head, ears, nose, throat, lungs, lymph nodes, heart, abdomen and skin) at screening will be conducted to determine study eligibility. A modified physical examination will also be performed at Days 1, 8, 15, 29 and 57 and at the early termination visit if applicable. The symptom directed physical examinations will be performed based on signs and symptoms the subject has reported verbally and/or documented in the diary booklets. A symptom directed physical examination may also be performed if in the opinion of the Investigator if it is required.

Vital signs measured:

- Body temperature (degrees Celsius) aural
- Respiratory rate
- Pulse rate (sitting)
- Blood pressure (sitting)

Height and body weight will be measured and documented at the Screening visit.

7.4.2 Electrocardiograms

The ECG recordings in this clinical trial will be performed in a standardised manner as outlined in the Study Reference Manual. Repeat measurements will be performed if there are any clinical abnormalities observed or artefacts are present. All ECG recordings will be reviewed by the Investigator or nominee.

The ECG recordings will be performed once the subject has been resting semi-supine for at least 10 minutes and will be measured in triplicate over approximately 3 minutes. The following parameters will be reported: QRS, QT, QTcB, RR and PR intervals.

The formula for calculating the corrected QT interval in respect to the heart rate will also be calculated using either Bazett or Fredericia formulas. If this isn't automatically calculated by the ECG machine, the following formulas will be used:

- Bazett's formula: $QT / (RR)^{0.5}$
[Observed QT interval divided by root of RR interval, in seconds]
- Fridericia's formula: $QT / (RR)^{0.33}$
[Observed QT interval divided by cube root of RR interval, in seconds]

Any clinically significant out of range or arrhythmia alarms will be printed out and recorded in the subject's CRF and reported as AEs if occurring after screening.

7.4.3 Blood and urine samples for laboratory tests

Blood and urine will be collected at all visits and should be within the visit window (see 7.2) Detailed instructions on the handling and processing of specimens are located in the Study Reference Manual. The following will be collected at the times specified in Section 7.3:

Haematology:	Haemoglobin, haematocrit, red blood cell (RBC) count , white blood cell and differential white blood cell count, platelet count, mean corpuscular volume (MCV), mean corpuscular haemoglobin concentration (MCHC), erythrocyte sedimentation rate (ESR).
Chemistry:	Sodium, potassium, chloride, bicarbonate, BUN, creatinine, total protein, albumin, serum amylase, phosphorus, AST, ALT, GGT, alkaline phosphatase, total bilirubin, glucose, CPK, calcium, uric acid, C-reactive protein (CRP)
Viral Serology:	HIV, HCV and HBV (at screening). HIV testing will be repeated after screening if there is a clinical suspicion that a subject may be at risk of infection.
Immunological:	HLA typing if required. HLA typing does not need to be repeated if part of medical record from an appropriately accredited laboratory, anti-CCP2 titre (if required), Rheumatoid Factor, Tetramer analysis (Collagen II peptide and other RA autoantigens), Exploratory immune assays (measures of humoral and T cell responses e.g. Interferon-gamma (IFN- γ) enzyme linked immunospot (ELIspot) assays, T-cell responses specific for RA autoantigens)
Urinalysis:	Protein, glucose, blood and microscopy (if abnormal).
Urine Pregnancy:	Human chorionic gonadotropin.
Serum pregnancy:	Human chorionic gonadotropin.
Pharmacokinetics:	Calcitriol concentration in plasma and pharmacokinetic indices

7.4.4 Handling and processing of biological specimens

All personnel involved in collecting and handling biological specimens should follow appropriate standardised operating procedures for handling biohazardous materials including those procedures recommended by the national regulatory authority.

Laboratory safety evaluations, including haematology, clinical chemistry, urinalysis and coagulation will be performed by the sites local laboratory.

Immunological testing will be performed by:

- Tetramer Analysis: Precision for Medicine
- HLA Typing: Victorian Red Cross
- Rheumatoid factor: Pathology Queensland
- Anti-CCP : Pathology Queensland
- ELISpot Analysis : Precision for Medicine
- Exploratory Immune Assays: [name]
- Microbiome analysis: Australian Centre for Ecogenomics at UQ

Pharmacokinetic analysis (plasma calcitriol concentration) will be performed by: Eurofins ADME BIOANALYSIS.

All contact details for laboratories are outlined in Section 2.0 of this protocol and in the Study Reference Manual.

7.4.5 Diary booklets

Subjects will be provided with a diary after each administration of DEN-181 to collect injection site reactions.

Injection Site Reaction Diary:

The aim of this diary is to collect information about injection site reactions for 3 days following the administration of IMP. Information that is to be collected includes the presence of:

- Pain/tenderness;
- Swelling/induration;
- Erythema; or
- Other findings.

Subjects will be provided with a ruler to enable the subject to measure and record the size of any injection site reactions that occur. Subjects will measure the longest diameter of any reaction area. Instructions on the measurement of reactions will be provided to the subjects within their diary booklet.

The Injection Site Reaction Diaries will be issued at visit 2 and collected at visit 3 for Parts A and B. In part B only, Diaries will also be issued at visit 3 (collected at visit 4) and visit 4 (collected at visit 5). The site staff will check that the diary is complete and legible while the patient is present after collection to ensure any clarifications can be performed.

7.4.6 Pregnancy tests

Serum pregnancy testing will be conducted for female subjects of childbearing potential at screening (visit 1). Before administration of the IMP (visit 2), visit 3 (Part B only), visit 4 (Part B only) and at the end of the study (visit 6) a urine pregnancy test will be performed.

If the urine pregnancy test is positive at visit 2, visit 3 (Part B only) or visit 4 (Part B only) a serum pregnancy test will be conducted to confirm the urine-based test and the IMP will not be administered until a negative result is obtained. If the serum pregnancy test is positive, the patient will be excluded or withdrawn from the study.

If the result of the urine pregnancy test is positive at visit 6, a serum pregnancy test will be conducted to confirm the urine-based test. If the serum-based test is positive at any visit, procedures for reporting a Clinical Trial Pregnancy will be performed.

7.4.7 DAS28CRPv4 evaluation

The DAS28CRPv4 is a frequent outcome measure used in rheumatoid arthritis therapeutic trials and is also used to guide treatment decisions. The DAS28CRPv4 related assessments and score calculation will be performed at all visits. See Appendix 2.

7.4.8 Microbiome Testing

Oral swabs will be taken at Baseline (visit 2) and at visit 6 so as to allow testing for the types of microbial communities found in these areas. Sequencing will be undertaken at Australian Centre for Ecogenomics at UQ.

8 INVESTIGATIONAL MEDICINAL PRODUCT

8.1 Randomisation process

This is a Phase I, randomised, double-blind, placebo-controlled, single-centre, single-dose escalation and multiple dose, dose-ranging parallel group study to investigate the safety, tolerability and pharmacodynamics of subcutaneously administered DEN-181 in adult patients with ACPA+ rheumatoid arthritis on stable treatment with methotrexate. The study is to be performed in two parts.

Part A is a single centre, randomised, double blind placebo controlled single-dose dose escalation study. Three cohorts will be dosed. Subjects in each cohort will be randomised to receive either DEN-181 or placebo in a 2:1 ratio of active to placebo with the respective groups having the following sample sizes:

- Group 1: 6 (4 active, 2 placebo)
- Group 2: 6 (4 active, 2 placebo)
- Group 3: 6 (4 active, 2 placebo)

A randomisation scheme will be prepared in advance by the study statistician using a computer generated system according to relevant SOPs. The scheme will have the property that within each dose cohort the initial sentinel cohort of 1 active and 1 placebo will be randomised prior to randomising the remaining subjects. That is:

- Group 1: Sentinel (1 active, 1 placebo) followed by 3 active and 1 placebo
- Group 2: Sentinel (1 active, 1 placebo) followed by 3 active and 1 placebo
- Group 3: Sentinel (1 active, 1 placebo) followed by 3 active and 1 placebo

Part B is a single-centre, randomised, double blind placebo controlled multiple-dose, dose-ranging parallel-group study. Two groups will be dosed. Subjects in each group will be randomised to receive either DEN-181 or placebo in a 3:1 ratio of active drug to placebo with the respective groups having the following sample sizes:

- Group 1: 20 (15 active, 5 placebo)
- Group 2: 20 (15 active, 5 placebo)

A randomisation scheme will be prepared in advance by the study statistician using a computer generated system according to relevant SOPs.

8.2 Blinding

Since DEN-181 is white and the placebo is clear, it will not be possible to blind the clinical staff who administer the dose. At the commencement of the study, the un-blinded staff who will administer IMP and back-up personnel will be identified and trained. Staff who administer IMP will not be permitted to be involved in patient assessments or management throughout the trial. Additionally they will not discuss what they believe the subject is receiving with either the subject or other staff members.

All other site staff and the subject will be blinded to the study allocation between DEN-181 and placebo. The Sponsor and its representatives will also be blinded to the treatment allocation throughout the course of the study. The investigational product administrators will make every attempt to ensure that both the subject and the blinded team members do not observe the subcutaneous injection as this may threaten the integrity of the blind. The subject may be asked to turn away during the injection. Similarly, other blinded site staff will be instructed to not observe the administration of the investigational product or placebo. This will be highlighted during the site initiation visit and throughout the study.

An un-blinded monitor will perform drug accountability according to the Monitoring Plan.

The dose level will not be blinded.

8.3 Treatment allocation

The pharmacist or responsible party will prepare the treatment corresponding to the subject number in the randomisation plan. A period of no less than 7 days will elapse between administration of IMP to the sentinel patients in Part A and the start of treatment for remaining patients of the same cohort.

8.4 Un-blinding

8.4.1 Medical emergency

Code break envelopes will be provided to the clinical trial site. The Investigator may request the treatment assignment in emergency situations only. The breaking of the blind will only be sanctioned where knowledge of the study medication treatment will affect patient management. The Investigator will discuss the need to un-blind with the Sponsor prior to any un-blinding taking place, unless immediate knowledge of the treatment allocated is required for patient care.

If the code is broken, a note to file will be generated by the individual who broke the code explaining the reason and date that the blind was broken. Details of the person who authorised the code break, and the identity of the study product allocated to the subject must be included in this note and countersigned by the Investigator.

Reason(s) for un-blinding will be clearly documented and the details included in the study report.

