10.3.3.2 Investigator reporting requirements for SAEs

An SAE may qualify for reporting to regulatory authorities if the SAE is considered to have a possible causal relationship to the study product, and is unexpected (Suspected Unexpected Serious Adverse Reaction [SUSAR]) based upon the current Investigator's Brochure. In this case for multi-centre studies, all Investigators will receive a formal notification describing the SAE.

Where this is required by local regulatory authorities, and in accordance with the local institutional policy, the Investigator should notify (in writing) the Human Research Ethics Committee (HREC) which approved the study of the SAEs, according to HREC requirements as soon as is practical.

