10.7 Guidance for dose modification or discontinuation of treatment

To date, no specific toxicities have been identified that result from DEN-181 treatment. Any toxicities and/or abnormal laboratory findings should be investigated for aetiology and graded according to Appendix 1.

The following toxicity management will be followed:

- Grade 1 or 2: Patients may continue study treatment/placebo (except if they have an elevated temperature of >38 degrees Celsius or inter-current systemic illness). Dosing may be delayed for up to 7 days. Any dosing delays of >7 days may require that the subject is withdrawn after discussion with the Medical Monitor. Safety assessments will occur immediately prior to each dosing of IMP;
- Grade 3: Patients with any Grade 3 toxicity considered to be at least possibly related to treatment (i.e. treatment related events) should be evaluated carefully by the Investigator prior to continuing IMP treatment. Investigators may discuss individual cases with the Medical Monitor;
- Grade 4: Patients developing any Grade 4 toxicity should have treatment interrupted. The Investigator should contact the Medical Monitor to discuss the subject’s withdrawal.

Subjects will be withdrawn from treatment permanently should any of the following occur:

- Treatment related Grade 4 toxicity
- The need to take medication which could interfere with study measurements
- Subject unwilling to proceed and/or consent is withdrawn.

Where possible subjects who are withdrawn from treatment will remain on the study and attend the scheduled study visits, provided the Investigator deems it appropriate and the Sponsor approves.

Dosing will be stopped if suspected adverse drug reactions, changes to vital signs or clinical laboratory results are observed and these changes pose a significant health risk.

A corresponding adverse event will be captured within the CRF.

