For any subject experiencing any event (irrespective of severity) which, in the opinion of the Investigator, contraindicates further dosing in that subject and the event is considered to be at least possibly related to treatment (or where causality to study treatment cannot be ruled out – see Section 10.2.1), continued dosing of the subject should be interrupted. In all cases, the final treatment decisions, made in response to toxicity, are the responsibility of the Investigator. A careful evaluation of the potential risk/benefit will dictate the optimal therapeutic course. Should treatment be interrupted, re-initiation will follow review of the available safety data and in agreement with the Sponsor. There will be no dose reduction or modification.

If the Investigator deems that management of the patient's medical condition requires knowledge of the study treatment regimen, then the Medical Monitor must be contacted for consultation and the procedures described in Section 7.3 followed. If a patient dies from an event that is considered to be at least possibly related to treatment, continued dosing of all study participants should be interrupted until the SMC has reviewed the data.

Clinically significant suspected adverse drug reactions, and serious adverse events considered to be related to study procedures will be followed until resolved or considered stable. All subjects who experience a study drug related AE should be followed until resolution of the AE, even if the subject has discontinued study drug.

If an unscheduled interruption of study drug occurs, the study site should notify the Sponsor at the earliest possible time. In the event that a subject requires an unscheduled interruption of study drug under conditions other than those associated with toxicity, the case will be reviewed by the Sponsor to determine whether such a subject will be allowed to resume study drug.

Subjects withdrawn from study drug will be treated as deemed appropriate by the Investigator. Follow-up procedures should be performed and the appropriate CRFs should be completed.

The study may be terminated at any point in time at the discretion of the Sponsor.

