11 DATA SAFETY MONITORING

The Sponsor has convened a Safety Monitoring Committee charged with the review of safety data and dosing decisions during the conduct of the study.

The SMC will be responsible for reviewing safety data in Part A so as to allow dose escalation and enrolment of the next dose level. Dose escalation will be determined after each cohort has been enrolled and data are available through Day 15.

The SMC will also be responsible for a full review of all available safety data upon administration of Investigational Product to all subjects so as to assess whether it is safe to initiate Part B of the study. This safety review will be initiated upon receipt of safety data minimally up to at least the Day 15 visit for all study participants in Part A. At this time, all available data will be reviewed by the SMC and agreement to proceed to Part B formalised in writing.

Ad-hoc meetings will be scheduled immediately should any safety concerns arise at any time during the conduct of the study.

The treatment blind will not be broken for the purposes of SMC review, and the SMC will review only data blinded to treatment allocation.

Meetings will be convened to review aggregate and individual patient level data by injection regimen prepared as listings and tables. At a minimum, baseline patient characteristics, vital signs and adverse events will be provided.

Membership of the SMC will include the Investigator(s), Medical Monitor for the study and one company representative. An expert advisor on rheumatoid arthritis and/or clinical immunology will be invited, as appropriate. The Clinical Project Manager or other Sponsor designated staff will be invited to facilitate information dissemination and preparation of documentation of meeting outcomes and decisions.

Details of the membership function and decision making processes of the SMC for this study are set out in a separate SMC Charter.

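### After a possibly related death, the SMC review that ends the study-wide dosing pause has no sanctioned way to learn whether that patient received DEN-181 or saline

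*Protocol*

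**What the plan says.** Four sections of the Protocol bear on this.

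- **Section 8.4.1** supplies code-break envelopes to the site. "The Investigator may request the treatment assignment in emergency situations only", and "The breaking of the blind will only be sanctioned where knowledge of the study medication treatment will affect patient management". The only other code break is in section 8.4.2, after database lock.
- **Section 8.2** keeps the Sponsor and its representatives blinded for the whole study. The dose level is open, so the only hidden fact is active versus saline.
- **Section 10.7** says that after a death judged at least possibly related to treatment, "continued dosing of all study participants should be interrupted until the SMC has reviewed the data".
- **Section 11** says: "The treatment blind will not be broken for the purposes of SMC review, and the SMC will review only data blinded to treatment allocation". The committee consists of the Investigator(s), the Medical Monitor and one company representative. An RA or immunology adviser is invited as appropriate.

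Section 10.7 also tells the Investigator to follow Section 7.3 when knowledge of the treatment is needed. Section 7.3 is the visit schedule; un-blinding is in 8.4.

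**The concern.** The Protocol requires a decision that affects every participant and withholds the most informative fact about the case that triggered it. Once the patient has died, the sole ground in 8.4.1 is no longer available, because there is no management left to affect. Section 11 closes the committee's route and 8.2 closes the Sponsor's. Section 10.8 states that this is a first-in-man study with an uncharacterised adverse event profile, so the reviewers have no human safety record against which to judge causality.

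The sections also fit badly if the envelope was opened while the patient was alive. The Investigator may then know the allocation and sit on a committee that is confined to blinded data. Nothing says how that knowledge is to be handled.

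At stake is the quality of one interim safety decision. A review that cannot tell a death on DEN-181 from a death on saline may keep the study halted for a saline case, or weigh a DEN-181 case less heavily than it would with the fact in hand.

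**Working it through.** **1. Allocation (section 8.1) against the stated total (section 14.6).** Part A has three cohorts of 4 active and 2 placebo; Part B has two groups of 15 active and 5 placebo.

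- Active: 3 × 4 + 2 × 15 = 42
- Placebo: 3 × 2 + 2 × 5 = 16
- Total: 42 + 16 = 58, which reproduces the stated figure.

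**2. Routes to one patient's allocation before database lock, after a possibly related death.**

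| Route | Section | Available? |
|---|---|---|
| Investigator opens the envelope while the patient is alive | 8.4.1 | Yes, if it affects that patient's management |
| Investigator opens it after the death | 8.4.1 | No, the stated ground is gone |
| SMC asks for it | 11 | No, barred without exception |
| Sponsor asks for it | 8.2 | No, blinded throughout |
| End-of-study code break | 8.4.2 | Too late for the pause |

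**3. What the review does not know.** Let a be the active share in the patient's allocation block and RR an assumed relative risk of the event on DEN-181. For a single case,

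P(on DEN-181) = a × RR / (a × RR + 1 − a).

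The Protocol gives no RR, so a range is shown.

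| Patient | a | RR = 1 | RR = 2 | RR = 10 |
|---|---|---|---|---|
| Sentinel (1:1) | 0.50 | 0.50 | 0.67 | 0.91 |
| Rest of a Part A cohort (3:1) | 0.75 | 0.75 | 0.86 | 0.97 |
| Part B (15:5) | 0.75 | 0.75 | 0.86 | 0.97 |

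For example, a sentinel at RR = 2 gives 0.5 × 2 / (0.5 × 2 + 0.5) = 0.67. By allocation alone (RR = 1), the chance of placebo is therefore 1/2 for a sentinel and 1/4 for the others. Releasing the one allocation turns the probability into 0 or 1.

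**4. What a release would disclose about others.** Each Part A cohort is a sentinel pair (1 active, 1 placebo) followed by four patients (3 active, 1 placebo).

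- Sentinel case: the other sentinel is known at once.
- Placebo case among the four: the other three are all active, so all four are known.
- Active case among the four: 2 active and 1 placebo remain, so each remaining patient's chance of placebo moves from 1/4 to 1/3.

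**The case against.** The strongest reply is that blinded safety review is a deliberate and consistent choice. Sections 8.2, 8.4.1 and 11 all point the same way, and a blinded committee is not helpless. It can treat a possibly related death as a DEN-181 death until shown otherwise. By allocation that is right 75% of the time outside the sentinel pairs, and 86% to 97% of the time if the drug raises the risk 2- to 10-fold. A reader might infer that the committee would resume dosing after a DEN-181 death it could not recognise. The Protocol does not imply that; a cautious halt is at least as likely. This part of the reply stands, and it limits the consequence. It does not explain why the fact should be withheld from a review that the Protocol itself makes decisive.

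Three other inferences go too far.

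- *That the gap covers every serious reaction.* The explicit study-wide pause lifted by the SMC applies to death only. For a non-fatal event, 10.7 calls for a stop when a suspected reaction or an abnormal finding seriously endangers health, without saying whether one patient or the whole study is meant. A living patient's code can still be opened under 8.4.1.
- *That the safety conclusion of the trial is distorted.* The code is broken after database lock (8.4.2), and the safety set is analysed by treatment received (13.4.3), so the death is counted in the right arm.
- *That regulatory reporting is compromised.* Section 10.3.3.2 says only that "An SAE may qualify for reporting to regulatory authorities if the SAE is considered to have a possible causal relationship to the study product", with unexpectedness as a further condition. It is silent on unblinding, which may be handled in procedures not shown.

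It may also be said that the SMC Charter, which is not shown, covers the point. It could not allow a code break for SMC review without contradicting section 11.

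**Conclusion.** The concern holds for one situation: the SMC review required by 10.7 after a death judged at least possibly related to treatment. If the envelope was not opened beforehand, the committee cannot learn the allocation. If it was, one member may know while the committee as a whole must not. The uncertainty left is a 1/2 chance of placebo for a sentinel and 1/4 otherwise, assuming that the drug does not change the risk; it shrinks to between 1/3 and about 1/10 for a sentinel, and to between about 1/7 and 1/30 otherwise, at an assumed relative risk of 2 to 10. The final analysis and the sample size are not affected.

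This is a recommended correction. It rests on reading patient management in 8.4.1 as management of the patient concerned, which the emergency setting of that section supports.

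**What to change.** Reconcile sections 8.2, 8.4.1, 10.7 and 11. In 8.4.1, add a second, restricted ground: for the SMC review that 10.7 requires after a possibly related death, that single subject's allocation may be released, with documentation, to a named recipient who does not assess patients. Put a matching exception in 8.2 and section 11. State how the recipient's knowledge enters the review, and how an Investigator who already knows the code from the emergency takes part. Correct the cross-reference in 10.7 from Section 7.3 to 8.4. The pause and resumption rules themselves are for the sponsor and need not change for this purpose.

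The recipient needs care. The RA or immunology adviser is not a standing member. The Medical Monitor takes part in toxicity and withdrawal discussions (10.5, 10.7) and may count as a Sponsor representative under 8.2. The sponsor should name someone to whom neither difficulty applies, or write the exception so that it covers the person chosen.

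The cost is a few sentences in the Protocol and the SMC Charter. The real downside is disclosure in small blocks: one release can reveal the other sentinel, or all four remaining cohort members if the case is their placebo patient. The exception should acknowledge this and keep the information with the named recipient as far as the review permits.
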